6.4 Multiple Comparisons and Multiplicity

This study is descriptive in nature and informal testing of multiple endpoints may be performed. Given the exploratory nature of the comparisons, no adjustment of Type I error is planned.

7 GENERAL CONSIDERATIONS

7.1 Reference Dates

- Screening date is defined as the eCRF provided date on which a subject was screened for trial entry and informed consent was obtained.
- Treatment start date is defined as the date of first dose of CST-2032 or matching placebo. Each treatment period will have a treatment start date (i.e., in order to determine AEs occurring during a treatment). Subjects commence dosing of CST-107 or matching placebo 1 day earlier and this will be considered Day -1.
- Treatment end date is defined as the date of last dose of study drug.
- Safety data, such as AEs and laboratory assessments will use the treatment start date as a reference date.
- Study day will be based on treatment start date as a reference date.

7.2 Study Day and Duration Variables

Study day or duration calculations will generally be defined as the following, assuming non missing dates:

- date of interest – reference date + 1, when the date of interest \geq reference date;
- otherwise, date of interest – reference date.

If either date is missing, reference day or duration calculations will not be performed. Date imputation will be performed as identified in Section 6.4. In general, study day will be based on the treatment start date as the reference. As such, study day would either have a negative value if collected before dosing or a positive value if collected on or after the day of drug dosing; there will be no study day zero.

Duration of time is dependent on reference dates and will be calculated in a manner similar to that of the reference date calculation, assuming that dates of interest will strictly follow reference dates (e.g., no negative values). For example, duration of time in study is defined as the end of study date – informed consent date + 1. Duration of treatment is defined as treatment end date – treatment start date + 1, where treatment end date is the date of last dose of study drug.

7.3 Baseline and Post-Baseline Changes

Unless stated otherwise, baseline and post-baseline change values will be based on the following:

- Baseline will be based on the last non-missing value collected prior to or on the treatment start date and time. Post-baseline values will be those collected after the treatment start date and time.
- Change from baseline is defined as: value – baseline value.

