1.1.2. Rationale for CST-107 Dose Selection

CST-107 (nadolol) is included in this study to attenuate the peripheral effects most commonly caused by CST-2032 and other β_2 -AR agonists. In the phase 1 clinical trial with CST-2032, a range of doses of CST-107 was evaluated to determine the minimum dose at which the observed peripheral β_2 -AR agonist clinical signs (including increased heart rate, palpitations, tremors, decreases in potassium and increases in blood glucose) were attenuated or eliminated. While the latter effects were substantially mitigated following 1 mg CST-107, more robust inhibition of the peripheral effects was observed with 3 mg CST-107. A dose level of 3 mg CST-107 (nadolol) is in marked contrast to the usual initial dose for hypertension which is 40 mg CST-107 tablets once daily. The usual maintenance dose for nadolol is 40 or 80 mg administered once daily and doses up to 240 or 320 mg administered once daily may be needed.

Separate assessments in the CLIN-007 study show that only 2-3% of the plasma concentration of CST-107 is detected in cerebrospinal fluid of healthy volunteers. Furthermore, effects of CST-2032 on measures of cognition using CANTAB and cerebral perfusion were observed in the presence of CST-107.

Taken together, these data support the use of CST-107 as a peripherally restricted β_2 -AR antagonist to mitigate peripheral effects of CST-2032, e.g., on heart rate, while preserving potential central effects on cerebral perfusion, cerebral metabolism, pupillary light reflex, and cognition.

Based on the above experience, after completion of all scheduled assessments and baseline measures on Day -1, an initial dose of 3 mg CST-107 or matching placebo will be administered on Day -1 of each treatment period to provide systemic CST-107 exposure prior to the T_{max} of CST-2032 on Day 1. On subsequent dosing days (Days 1 through 14) in

Treatment periods 1 and 2, 3 mg CST-107 will be co-administered with 3mg CST-2032 as, after the first dose, trough concentrations of CST-107 are predicted to be sufficient to attenuate peripheral effects of CST-2032.

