8.5. Statistical Methods

Statistical analyses will be performed using SAS 9.4 or higher. Continuous data will display number of subjects, means, standard deviations, median, minimum, and maximum.

Categorical data will display frequency counts and percentages. Unless specified otherwise, confidence intervals will be displayed at the two-sided 95% confidence level.

Summaries of disposition and baseline data will be summarized by treatment, disease criteria (MCI vs. mild dementia), treatment sequence and overall. Summaries of safety, and pharmacodynamic measures (e.g., effects of treatment on CANTAB, pVFT, DSST, Color

Trails Test, FERT, GDS-30, SAS-6, CAARS, ADCS-CGIC) will be presented by treatment overall. PK of CST-2032 and CST-107 will be presented by treatment and treatment sequence. A limited subset of summaries may be presented by treatment and treatment sequence and/or period and overall.

For analysis purposes, Baseline will be defined as either the pre-dose measurement(s) taken within each of the study periods, or as the last measurement(s) before the first dose received. This will be detailed in the SAP for each parameter. All data will be listed.

Any changes in the planned analysis will be described and documented in the SAP and/or clinical study report.

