14.2.2.9.2	Secondary Endpoint: Montreal Cognitive Assessment Observed and Change from Baseline Results by Timepoint – Subgroup Analysis	Full Analysis Set
14.3.1.1*	Overall Summary of Adverse Events	Safety Set
14.3.1.2*	Treatment-Emergent Adverse Events by System Organ Class and Preferred Term	Safety Set
14.3.1.3*	Treatment-Emergent Serious Adverse Events by System Organ Class and Preferred Term	Safety Set
14.3.4.1.1*	Hematology – Observed Results and Change from Baseline by Timepoint	Safety Set
14.3.4.2.1*	Clinical Chemistry – Observed Results and Change from Baseline by Timepoint	Safety Set
14.3.4.2.2	Clinical Chemistry – Shifts from Baseline by Timepoint	Safety Set
14.3.5.1*	Vital Signs – Observed Results and Change from Baseline by Timepoint	Safety Set
14.3.6.1*	Electrocardiogram (ECG) – Observed Results and Change from Baseline by Timepoint	Safety Set

* denotes outputs to be reviewed by the DSMB

The efficacy analyses may be performed on all subjects included in the interim analysis and/or, separately, for AD and/or PD subgroups in this set. Additionally, further analyses of PD-MCI, PD-MD, AD-MCI, and AD-MD subgroups may be undertaken in the efficacy analyses if sufficient subjects are enrolled. A final decision on the populations to be analyzed will be made prior to the

interim analysis based on the number of subjects enrolled with PD or AD, and within the further MCI or MD groups. For example, the Sponsor may elect to exclude a patient population from the interim analysis if the post-dose data are available for fewer than e.g., 25 subjects. The baseline and safety summaries will be performed on all subjects included in the interim analysis regardless of the patient population(s) selected for efficacy analysis.

To produce these outputs, a biostatistician and a statistical programmer from [REDACTED], separate from the primary study team, will be unblinded to treatment assignments and work within a restricted domain inaccessible to all other [REDACTED] members. No additional team members from [REDACTED] or CuraSen will become unblinded until after database lock and release of the live randomization list at the time of study completion. The unblinded statistician will be in attendance during the closed DSMB sessions for the purpose of presenting and interpreting the interim analysis results. Additional information regarding the roles, responsibilities, and objectives for the DSMB will be outlined within a DSMB charter, separate from this SAP.

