11.3 Vital Signs

Vital signs will include the following: systolic and diastolic blood pressure (mmHg); heart rate (beats/min), temperature (°C), and respiratory rate (breaths/min).

Observed values and changes from screening/baseline for vital signs will be summarized at each visit and time point. Summaries will be presented by treatment at the time of data collected (i.e., Placebo and CST-2032/CST-107). If multiple collections occur for the same visit and timepoint in two positions, the values will be averaged.

All vital sign data will be listed.

Box plots of observed results or change from baseline at each visit for heart rate, systolic blood pressure, and diastolic blood pressure results for each treatment group may be generated.

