² Visit to be conducted in the clinic, or other off-site location or at the subject's home according to site preference and capabilities. In addition, should there be factors and/or conditions which would make a site visit unnecessarily difficult and/or potentially unsafe for a subject, some visits and/or procedures may be performed by alternate arrangement, e.g., visits in the subject's home, virtual visits. The End of Study visit is to occur 7-12 days after last dose of study drug.

³ Subjects who withdraw from the study prior to completion of dosing should complete these Day 14 safety assessments at the time of

early withdrawal (EW).

4 The Color Trails Test should be completed after the CANTAB assessments (select sites only).

5 Vital signs to include orthostatic changes in BP and HR, respiratory rate, and oral/tympanic temperature. For assessments of orthostatic changes, BP and HR are obtained: a) after rest in a supine position for at least 5 minutes, and b) 1 minute after standing. Vital signs will be obtained at every study visit as follows:

- Screening
- Day -1 prior to administration of CST-107 or matching placebo in each treatment period
- Days 1, 7, and 14 of each treatment period:
 - Within 30 minutes prior to dosing of study drug (CST-2032+CST-107 or matching placebos),
 - Approximately 4 hours (\pm 30 minutes) after administration of study drug,
- End-of-Study Visit.

6 ECGs to be obtained in triplicate (separated by approximately 1 minute) after subject is supine for 5 minutes at the following timepoints:

- Screening
- 3 sets of triplicate ECG measures (i.e., 9 ECGs) on Day -1 prior to administration of CST-107 or matching placebo in each treatment period to thoroughly establish a baseline; the time between each set of 3 ECGs should be \leq 5 minutes.
- On Day 1 of each treatment period:
 - Within 30 minutes prior to dosing of study drug,
 - Approximately 1 hour after administration of study drug,
 - Approximately 2 hours after administration of study drug,
 - Approximately 4 hours after administration of study drug,
- Days 7 and 14 of each treatment period:
 - Within 30 minutes prior to dosing study drug,
 - Approximately 1 hour after administration of study drug,
 - Approximately 2 hours after administration of study drug,
 - Approximately 4 hours after administration of study drug,
- End-of-Study Visit,
- All ECGs will be evaluated by a central ECG reader.

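### The SAP's default rule sets the vital-sign baseline after the Day -1 CST-107 dose, so in the active period the baseline is not drug-free

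*SAP*

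**What the plan says.** Three parts of the plan together fix the vital-sign baseline.

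- **Reference point.** SAP 7.1: "Treatment start date is defined as the date of first dose of CST-2032 or matching placebo". Each period has its own start date, and the same section notes that CST-107 or its placebo begins one day earlier.
- **Default rule.** SAP 7.3: "Baseline will be based on the last non-missing value collected prior to or on the treatment start date and time". It applies unless another section overrides it.
- **Schedule.** SAP Appendix 2, footnote 5, lists vital signs at "Day -1 prior to administration of CST-107 or matching placebo in each treatment period" and again on Day 1 at "Within 30 minutes prior to dosing of study drug (CST-2032+CST-107 or matching placebos"). Footnote 18 places the Day -1 CST-107 or placebo dose after all of that day's assessments.

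The vital-sign section, SAP 11.3, adds only this: "Observed values and changes from screening/baseline for vital signs will be summarized at each visit and time point". It names no baseline visit.

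Protocol 8.5 allows baseline to be either the pre-dose measurement within a period or the last measurement before the first dose, and adds: "This will be detailed in the SAP for each parameter". Protocol 1.1.2 describes the intended order as "after completion of all scheduled assessments and baseline measures on Day -1, an initial dose of 3 mg CST-107 or matching placebo".

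**The concern.** The trial compares the CST-2032 and CST-107 combination with double placebo, and vital signs are part of the primary safety endpoint. A baseline taken after one active component has been given measures only what is added from that point. In the placebo period the corresponding baseline is free of same-period active drug. The two columns of the change table therefore start from different conditions.

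If CST-107 lowers heart rate or blood pressure, the change columns would hide that lowering and make a later rise on the combination look larger. The Day 1 pre-dose reading is also the only vital-sign reading taken on CST-107 alone. Used as baseline, it has no change value of its own.

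The table concerned is output 14.3.5.1, "Vital Signs – Observed Results and Change from Baseline by Timepoint". SAP 4.5 marks it for DSMB review if the optional interim analysis is run.

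**Working it through.** The plan states no figure to reproduce. The check is a trace of the rule, followed by simple algebra.

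**1. Order of events within a period** (SAP 7.1; Appendix 2, footnotes 5 and 18)

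| Step | Event | Active period | Placebo period |
|---|---|---|---|
| 1 | Day -1 vital signs | no study drug yet this period | no study drug yet this period |
| 2 | Day -1 dose | 3 mg CST-107 | placebo |
| 3 | Day 1 pre-dose vital signs | after CST-107 | after placebo only |
| 4 | Day 1 dose (treatment start) | CST-2032 + CST-107 | placebos |

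**2. Apply 7.1 and 7.3.** Treatment start is step 4. The latest reading up to that point is step 3, so step 3 is baseline in both periods. If step 3 is missing, the rule falls back to step 1, and the table would then mix the two kinds of baseline.

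**3. Look for an override.** The SAP 9.2 sections on CANTAB, verbal fluency, DSST, GDS-30, CAARS, SAS-6 and Color Trails each label Day -1 as baseline. SAP 11.4 averages as many as nine ECG tracings into one baseline value, which fits the three triplicate sets scheduled on Day -1 before CST-107. SAP 11.3 has nothing equivalent. Vital-sign heart rate and ECG heart rate would therefore have different baselines.

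**4. Effect on the contrast.** Let b be the drug-free baseline, e the CST-107 effect present at Day 1 pre-dose, and Ya and Yp later readings on active and placebo.

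- Active change = Ya - (b + e)
- Placebo change = Yp - b
- Difference = (Ya - Yp) - e

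A Day -1 baseline would give Ya - Yp, so the shift is -e. The documents give no value for e. For an assumed range:

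| Assumed e (bpm or mmHg) | Shift in active-minus-placebo change |
|---|---|
| 0 | 0 |
| -1 | +1 |
| -3 | +3 |
| -5 | +5 |

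The same shift applies to all five later on-treatment readings of the active period: Day 1 at 4 h (1), and Days 7 and 14 pre-dose and at 4 h (2 × 2 = 4).

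**5. Is CST-107 likely to be present at that reading?** Protocol 1.1.2 predicts that trough levels after the first dose are enough to blunt the peripheral effects of CST-2032. That implies drug on board. It does not imply a lower resting heart rate or blood pressure.

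The gap can be approximated. Let T be the Day 1 dose time.

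- Day 1 tests start at T + 2.5 to T + 3.5 h. Day -1 tests start at the same clock time ± 1 h, that is 1.5 to 4.5 h after T - 24 h.
- Assume a battery of 1 to 2.5 h with CST-107 given as soon as it ends. The dose then falls 2.5 to 7 h after T - 24 h.
- With Day 1 vital signs in the last 0.5 h before T, the gap runs from 24 - 7 - 0.5 = 16.5 h to 24 - 2.5 = 21.5 h.

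The conclusion does not depend on this interval.

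**The case against.** The case for leaving the rule alone has several parts.

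- **It is a permitted choice.** Protocol 8.5 allows a within-period pre-dose baseline, and SAP 7.1 openly acknowledges that CST-107 starts a day earlier. Section 7.3 also covers every parameter by default. This stands in part: there is no breach of the protocol, and the rule gives a definite answer. But a general default is not the parameter-by-parameter choice that Protocol 8.5 announces, and the answer it gives is unequal between the periods.
- **The information is not lost.** Observed values by timepoint appear in the same table, and ECG heart rate is tabulated separately. This stands: a reader could see a Day -1 to Day 1 shift. The change columns would still omit it, and blood pressure has no second source.
- **No decision depends on it.** SAP 11.3 plans descriptive summaries without a test, and the stopping criteria in Protocol 3.2 and 3.3 do not use mean changes. This also stands and limits the severity. The Protocol synopsis does, however, plan within-subject differences in change for primary endpoints, which is the quantity affected.
- **The effect may be nil.** Protocol section 1 puts the CST-107 doses at under 10% of the lowest approved 40 mg dose (3/40 = 7.5%) and expects them to act mainly on β2 receptors. The size is indeed unknown and could be zero.
- **Day -1 is not a perfect baseline.** Its vital signs have no fixed clock time, whereas Day 1 pre-dose matches the pre-dose readings on Days 7 and 14. True, but that weakness is the same in both periods, while the CST-107 effect is not.
- **Safety labs share the feature.** They do, but they have no Day -1 draw, so no alternative in-period baseline exists. For vital signs one is already scheduled.

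**Conclusion.** The concern holds. As written, the SAP measures vital-sign change from a reading taken after CST-107 in the active period and after placebo only in the other. Any CST-107 effect on heart rate or blood pressure at that reading is removed from the active change column alone and does not cancel against placebo.

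The shift equals minus the CST-107 effect. Under an assumed effect of 0 to -5 bpm or 0 to -5 mmHg systolic, it is 0 to +5 in the same unit. That range is an assumption, since the documents give no estimate. The direction and the asymmetry follow from the stated rule. Because the analysis is descriptive and observed values remain visible, this is a correction that should be made rather than a fault that undermines the trial.

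**What to change.** State in SAP 7.3 or 11.3 that the vital-sign baseline in each period is the Day -1 measurement before CST-107 or placebo, and tabulate Day 1 pre-dose as a post-baseline timepoint. This makes vital signs consistent with the cognitive endpoints and the likely ECG baseline, and gives the CST-107-alone reading a change value. The cost is a few lines of SAP text and one baseline flag. The Day -1 readings are already scheduled in both periods, so no data are added. The change should be made before any interim output is produced.

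Three related wording clarifications could go in at the same time; the finding does not rest on them:

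- SAP 11.4: name Day -1, as the mean of the nine tracings, as the ECG baseline. This is already the better reading.
- SAP 9.3: label Screening as the biomarker baseline for both periods. Read literally, 7.3 would make the Period 1 Day 14 sample the Period 2 baseline.
- SAP 11.2: state that safety labs have no Day -1 draw, so their Day 1 pre-dose baseline follows CST-107 in the active period.

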5.3.3. Clinical Laboratory Analysis

The following laboratory assessments will be performed at timepoints detailed in the [Schedule of Events](#):

Hematology: hematocrit, hemoglobin, mean corpuscular hemoglobin (MCH), mean corpuscular hemoglobin concentration (MCHC), mean corpuscular volume (MCV), platelet count, red blood cell (RBC) count, and white blood cell (WBC) count with differential, reticulocyte count.

Chemistry: albumin, alkaline phosphatase (ALP), alanine aminotransferase (ALT), aspartate aminotransferase (AST), BUN, calcium, bicarbonate, serum creatinine, creatine phosphokinase (CPK), glucose, lipase, amylase, phosphate, potassium, sodium, total bilirubin, total cholesterol, total protein, triglycerides, and uric acid.

Urinalysis: Appearance, occult blood, glucose, leukocyte esterase, nitrite, pH, protein, urobilinogen by dipstick; a reflex microscopic urinalysis will be performed if dipstick protein, nitrite, leukocyte esterase, or occult blood results are positive.

Calculated creatinine clearance according to the Cockcroft-Gault equation: To be determined at Screening only.

Serologies for HIV, hepatitis B, and hepatitis C: HbsAg, HbsAb, and HCV Ab (Screening only). If these results indicate potential infection, the PI must refer the subject for counselling and treatment as per institution policy and procedures.

SARS-CoV-2: Conducted at Screening by central lab. After Screening, the test may be conducted according to current local COVID management procedures.

Pregnancy Tests: Serum β -hCG for all female subjects of childbearing potential at Screening; serum or urine pregnancy test for women of childbearing potential on days noted in the [Schedule of Events](#). Positive urine pregnancy tests must be confirmed by a serum test.

Urine Drug Screen: Tests for drugs of abuse.

Alcohol breath test.

CST-2032 and CST-107 PK samples: Plasma samples will be collected for PK analysis on Day 7 of each treatment period for analysis of CST-2032, CST-107 and possible metabolites. Samples may be stored for up to 2 years.

Disease Biomarkers: Whole blood will be collected for analysis of genetic variants including but not limited to APOE4, LRRK2, and GBA (optional and where applicable) during screening, and plasma will be collected during screening and on Day 14 for analysis of neurodegeneration biomarkers (may be stored for up to 5 years).

Instructions on blood and plasma sample processing and shipping can be found in the Laboratory Manual.

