A bar plot of the least square mean change of the Part 2 completion time with error bars of the standard error will be produced, separated by AD and PD.

All Color Trails Test data will be listed.

Montreal Cognitive Assessment (MoCA)

Details of MoCA are outlined in section 8.4 of this SAP. The MoCA will be collected at Screening (Baseline) and Day 14 of each treatment period. Summary statistics of the MoCA-MIS Score and MoCA Total Score and change from baseline will be presented. A mixed model with change from baseline as the outcome, baseline as a covariate, fixed effects for treatment sequence, period, timepoint (i.e., Day 14), disease type, and treatment, and subject as a random effect will be

analyzed. LS mean, LS mean difference and its associated p-value will be reported. AR1 and CS covariance structures may be explored if there are convergence issues. The effect size will be estimated using Cohen's D: difference in means / pooled SD. This analysis will be performed using AD and PD as subgroups, and again using AD-MCI, AD-MD, PD-MCI, and PD-MD as subgroups.

All MoCA data will be listed.

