9.3 Exploratory Endpoints and Analyses

The FAS will be used for all exploratory endpoint analyses unless stated otherwise.

Neurodegenerative Biomarkers

Neurodegenerative biomarkers including neurofilament light chain, total and phosphorylated tau protein, and amyloid- β (A β) peptides will also be collected at Screening and Day 14 of each treatment period. If data is available descriptive statistics of the neurodegenerative biomarkers and change from baseline to Day 14 will be summarized. Additionally, genetic biomarkers including APOE4, LRRK2, and GBA may be collected at Screening and descriptive statistics may be tabulated if numeric. All biomarker data will be listed.

Z-scores

Z-scores will be calculated for the observed values of select CANTAB, pVFT, and DSST endpoints using the formula: $z = (\text{observed value} - \text{normative mean}) / \text{normative SD}$. Normative means and standard deviations can be found in Appendix 3, and specifics on which parameters will be used in z-score derivations (ATT2BDM, PALTEA, RTIFMDRT, SSTSSRT, and VRMFR11D) are in section 9.2 in the CANTAB section. Z-scores will also be derived for the Alphabet and Category total scores of pVFT and the DSST total score. For the endpoints of PALTEA, RTIFMDRT and SSTSSRT, in which higher scores reflect poor performance, the sign of z-scores will be reversed by multiplying the calculated z-score by -1. Hence a positive z-score will reflect an outcome better than the norm and a negative z-score will reflect an outcome worse than the norm. In the case of the adaptive tracking test in the CANTAB, normative data are from prior studies conducted by CuraSen. For endpoints for which multiple norms are shown in Appendix 3, pooled estimates of the normal mean and SD, weighted by the sample size, will be used to calculate the z-scores. Z-scores for DSST will use norms based on the age of the subject. Normative data for the CANTAB, VFT, and DSST endpoints are summarized in Appendix 3. Normative data for the verbal fluency tests, DSST and most of the tests within the CANTAB are defined from published studies in which the tests were administered in an approximately similar manner as the CLIN-011 study. Normative data are based on untreated, approximately age matched cognitively normal populations, except for the Stop Signal Test where data are only available for a young adult population are available.

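### SAP 9.3 names no baseline for the plasma biomarkers, so the SAP 7.3 default, read literally, makes the Period 1 Day 14 on-treatment sample the Period 2 baseline

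*SAP*

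**What the plan says.** **Sampling.** Protocol 5.3.3 states that "plasma will be collected during screening and on Day 14 for analysis of neurodegeneration biomarkers". SAP 9.3 agrees: its list of markers ends with amyloid-β, and these "peptides will also be collected at Screening and Day 14 of each treatment period". The schedules of events in both documents show no biomarker draw on Day -1 or Day 1 of either period.

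**Planned analysis.** If data are available, SAP 9.3 provides descriptive statistics, and "change from baseline to Day 14 will be summarized". It does not say which visit is the baseline.

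**Default rule.** Where nothing else is stated, SAP 7.3 applies: "Baseline will be based on the last non-missing value collected prior to or on the treatment start date and time". It adds: "Change from baseline is defined as: value – baseline value". SAP 7.1 defines treatment start as the first dose of CST-2032 or its placebo and says: "Each treatment period will have a treatment start date".

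**How similar measures are handled.** MoCA has the same visit pattern, and SAP 9.2 names its baseline: "The MoCA will be collected at Screening (Baseline) and Day 14 of each treatment period". The SAP labels Screening as baseline in the same way for ADCS-CGIC (9.2) and C-SSRS (11.6).

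**What the protocol foresaw.** Protocol 8.5 allows two kinds of baseline: a pre-dose measurement within each period, or the last measurement before the first dose received. It leaves the choice for each parameter to the SAP. Protocol 2.4 and SAP 3 define the biomarker endpoint as a comparison of values before and after treatment.

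**The concern.** No biomarker value exists after washout and before Period 2 dosing. A programmer who applies SAP 7.3 with the Period 2 treatment start from SAP 7.1 will take the latest earlier value, which is Period 1 Day 14. In the placebo-first sequence that does little harm, because the sample was taken on placebo. In the active-first sequence it was taken on drug, so the Period 2 placebo change includes recovery from the active effect and carries the opposite sign to it. A by-treatment summary would then subtract a placebo change that has been pushed away from zero by the drug itself. Describing the effect of treatment on these biomarkers is one of the two stated exploratory objectives.

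**Working it through.** The documents give no figure on this point to reproduce: no biomarker effect size, no variance and no washout time for the markers. The size is therefore worked out algebraically under stated assumptions.

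**Inputs from the documents**
- Two sequences, active-placebo and placebo-active, allocated 1:1 (protocol 7.2.1, SAP 4.2); about 60 subjects, so about 30 per sequence.
- Biomarker samples at Screening, Period 1 Day 14 and Period 2 Day 14.
- Washout of 7 to 21 days, extendable. With 14 days of Period 2 dosing, Period 2 Day 14 falls roughly 21 to 35 days after the last Period 1 dose (7 + 14 to 21 + 14).

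**Assumptions**
- Untreated level 0; active effect at Day 14 equal to d.
- A share c of the Period 1 active effect is still present at Period 2 Day 14, with c from 0 (full washout) to 1 (full persistence).
- Complete data. Drift common to both sequences cancels when they are balanced.

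**Literal SAP 7.3 rule (Period 2 baseline = Period 1 Day 14)**
- Active-first: active change d; placebo change cd - d.
- Placebo-first: placebo change 0; active change d.
- Mean active change: (d + d)/2 = d. Mean placebo change: (cd - d + 0)/2 = -0.5(1 - c)d.
- Active minus placebo: d + 0.5(1 - c)d = d(1.5 - 0.5c).

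**Screening baseline in both periods**
- Active changes d and d; placebo changes cd and 0.
- Active minus placebo: d - 0.5cd = d(1 - 0.5c).

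| c | Literal rule | Screening baseline |
|---|---|---|
| 0 | 1.50d | 1.00d |
| 0.25 | 1.375d | 0.875d |
| 0.5 | 1.25d | 0.75d |
| 1 | 1.00d | 0.50d |

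The literal rule overstates d by 0.5(1 - c)d. A Screening baseline understates it by 0.5cd, which is ordinary carryover. The two errors are equal in size at c = 0.5. Above that the literal rule lies closer to d, but only because its error and carryover offset each other.

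**Sensitivity of the literal rule at c = 0**
- If a fraction p of each sequence drops out before Period 2, the mean placebo change is -d(1 - p)/(2 - p). The difference is then 1.474d, 1.444d and 1.412d for p = 10%, 20% and 30%.
- A 32:28 split in favour of active-first gives d + (32/60)d = 1.533d; 28:32 gives 1.467d.
- Within the active-first sequence alone, or in Period 2 alone, the difference is d - (-d) = 2d. Within the placebo-first sequence it is d.

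If d = 0, every one of these contrasts is zero in expectation.

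**The case against.** The strongest reply is that the sponsor plainly meant Screening. Protocol 8.5 permits only a within-period pre-dose value or the last value before the first dose, and Period 1 Day 14 is neither. The endpoint compares values before and after treatment. SAP 2 says the SAP is to be read with the protocol. SAP 7.3 speaks of the treatment start date in the singular, and SAP 7.1 gives a purpose for the period-specific dates: "Each treatment period will have a treatment start date (i.e., in order to determine AEs occurring during a treatment". This is good evidence of intent, but it does not cure the text. Protocol 8.5 hands the choice to the SAP, parameter by parameter, and the SAP makes none for biomarkers. SAP 7.1 also applies the treatment start date to laboratory assessments and study day, so its use is not confined to adverse events.

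A second reply is that the pooled contrast is not a planned estimate. This largely stands. SAP 9.3 specifies no biomarker model, LS mean difference or p-value. The protocol synopsis promises the drug-minus-placebo difference for primary and secondary endpoints only. The SAP 6.1 default is to summarize by disease type, sequence and overall. SAP 9 does present efficacy data by treatment at the time of collection, so by-treatment change tables are possible, and a reader would compare their columns.

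A reader might also infer that the rule reaches back to Period 1 Day 14 for any test with a missing Period 2 Day -1 value. The documents do not support that. SAP 9.2 labels Day -1 of each period as Baseline for CANTAB, pVFT, DSST, GDS-30, CAARS, SAS-6 and Color Trails, and those labels override the default just as the Screening label does for MoCA. The fallback matters only where no baseline visit is named. Safety labs are an example: SAP 11.2 names none, and the only scheduled Period 2 pre-dose lab is on Day 1. If that is missing, the default can select the Period 1 Day 14 sample, drawn about 4 hours after dosing.

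**Conclusion.** The gap is real and should be closed. Read as written, SAP 7.1, 7.3 and 9.3 together give a Period 2 biomarker baseline taken on treatment, in conflict with protocol 8.5 and the endpoint definition.

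Its size is conditional. For changes pooled by treatment with complete 1:1 sequences, the difference is d(1.5 - 0.5c): 50% too large at full washout, shrinking to no excess if the effect fully persists. A reader might take 50% as an established bias or an upper bound. It is neither. It rests on full washout, balance and complete data, moves with dropout and sequence split, and reaches 100% in the active-first sequence or in Period 2 alone. The documents give no value for d or c.

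Nor do they support the inference that a planned test would be inflated or a false positive produced. The analysis is exploratory, conditional on data being available, and descriptive, and no difference arises in expectation when there is no drug effect. If the programmers use Screening, as was probably intended, the problem does not arise.

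**What to change.** Two sentences in the SAP, before database lock:

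1. In SAP 9.3, name Screening as the biomarker baseline for both treatment periods, as SAP 9.2 does for MoCA.
2. In SAP 7.3, state that a value collected after dosing in Period 1 may not serve as a Period 2 baseline. This has effect only for parameters with no named baseline visit.

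Comparing the two Day 14 values directly within subject is an equivalent option for subjects with both samples, because a common Screening value cancels from the difference in changes.

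Neither change needs a new sample, visit or subject. Neither removes ordinary carryover: with a Screening baseline the pooled difference is still d(1 - 0.5c). A true period-specific baseline would require a Period 2 pre-dose biomarker sample, which the schedule does not contain.
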